1.7 Assessment and management of risk

Exercise carries a very small risk of complications. All participants will be assessed for any underlying health conditions or severe complications related to COVID-19. Participants will be excluded from the study at the eligibility stage where exercise is clearly contraindicated, as assessed by a clinical member of the research team. A further assessment will be undertaken by the REGAIN practitioner, through discussion with the patient about their current health, at the time of the initial online intervention assessment. Any additionally identified contra-indications at this stage will result in withdrawal from the study. The REGAIN practitioner will advise on an exercise regime appropriate for each participant's ability. All participants will be advised to have another person nearby for the initial exercise sessions. We will encourage this wherever possible.

All intervention sessions will be led by staff experienced in assessment, prescription and delivery of exercise for multi-morbid clinical populations.

For the exercise programme, weekly troubleshooting will assess safety, progress, changes to health, and any adverse effects. This will take place during a 10 minute 'debrief' after each live online exercise session every week. Participants will have the opportunity to attend the troubleshooting session at least weekly to discuss any issues with the REGAIN practitioners and other participants. There will also be time to discuss these issues after each of the group behavioural sessions, and participants may contact the REGAIN practitioners or the study team via email or telephone with any further queries.

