Safety: All supervised sessions will be led by staff experienced in assessment, prescription and delivery of exercise for multi-morbid clinical populations. Pre- and post-exercise session poll questions will be completed by participants during each supervised session to capture any adverse events during the session and since the previous supervised session. Weekly troubleshooting after the live exercise sessions and the group behaviour change sessions will assess safety, progress, health, and any adverse effects. Participants will be advised to initially have another person nearby during exercise. If a participant fails to attend two consecutive intervention appointments a REGAIN practitioner will attempt to contact them via telephone or email in order to ascertain their welfare.

Intervention/control delivery: The multicentre REGAIN study will be delivered nationwide from a single central study 'hub'. The UHCW community exercise rehabilitation centre at Atrium Health delivers NHS cardiac, pulmonary, vascular, heart failure, cancer and other long-term condition rehabilitation services for Coventry and surrounding areas. Further, it is a clinical academic centre of excellence currently co-ordinating and delivering a number of nationally funded clinical exercise rehabilitation trials. The centre has the capacity, infrastructure and multi-disciplinary expertise to deliver the REGAIN study. Practitioners trained in the REGAIN intervention will be able to deliver the programme to groups of participants anywhere in the country using pre-recorded and live exercise and behaviour change sessions.

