4.2.2 Recording Adverse Events

Participants in the intervention group will have the opportunity to indicate whether or not they have experienced AEs by completing both pre- and post-exercise session poll questions. Responses indicating the participant has potentially experienced an adverse event will be evaluated by the practitioner and the participant contacted to confirm the details. Practitioners should also monitor for any information volunteered by a participant at any time during a live exercise session. Participants in the intervention group will also have contact details (generic email address and phone number) for the study team and practitioners. Whilst participants will not be actively encouraged to report AEs via this route, they may seek advice and help from the team which may result in AEs being disclosed/discussed. Any AEs will be recorded on the AE log unless they fulfil the criteria for a 'Serious Adverse Event' in which case they will be reported to WCTU via the SAE form (see section 14.2.3 below).

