4.3 Responsibilities

Practitioners:

Checking for AEs when participants attend for exercise session or via pre- and post-exercise poll responses:

- 1. Using clinical judgement in assigning seriousness and causality
- 2. Ensuring that all SAEs are recorded and reported to the Sponsor via Warwick QA within 24 hours of becoming aware of the event and provide further follow-up information as soon as available. Ensuring that reported SAEs are chased with WCTU if a record of receipt is not received within 2 working days of initial reporting.

Chief Investigator (CI) / delegate or independent clinical reviewer:

- 1. Clinical oversight of the safety of patients participating in the study, including an ongoing review of the risk / benefit.
- 2. Using clinical judgement in assigning causality
- 3. Immediate review of all related and unexpected SAEs
- 4. Review of specific SAEs in accordance with the study risk assessment and protocol as detailed in the Trial Monitoring Plan.
- 5. Production and submission of annual reports to the relevant REC.

Sponsor or delegate:

- 1. Central data collection and verification of SAEs, according to the study protocol.
- 2. Expectedness assessment of related SAEs
- 3. Reporting safety information to the CI, delegate or independent clinical reviewer for the ongoing assessment of the risk / benefit according to the Trial Monitoring Plan.
- 4. Reporting safety information to the independent oversight committees identified for the study (Data Monitoring Committee (DMC) and / or Trial Steering Committee (TSC)) according to the Trial Monitoring Plan.

- 5. Expedited reporting of related and unexpected SAEs to the REC within required timelines.
- 6. Notifying Investigators of related and unexpected SAEs that occur within the study.

Trial Steering Committee (TSC):

In accordance with the Trial Terms of Reference for the TSC, periodically reviewing safety data and liaising with the DMC regarding safety issues.

Data Monitoring Committee (DMC):

In accordance with the Trial Terms of Reference for the DMC, periodically reviewing unblinded overall safety data to determine patterns and trends of events, or to identify safety issues, which would not be apparent on an individual case basis.

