#### 6 SAFETY DATA

The frequency and percentage (%) of serious adverse events (SAE) and adverse events (AE) in the trial will be reported by treatment with the following details: the event type, severity assessment, expectedness and relatedness to intervention will also be summarised/analysed by treatment arm.

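### Once an intervention-arm participant stops attending, no specified question asks about non-serious adverse events that the protocol still requires to be recorded

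*Protocol*

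**What the plan says.** **What must be recorded.** Protocol 4.2.1 covers all intervention-arm AEs and serious AEs (SAEs) in a live or on-demand exercise session, supervised or not, and for 24 hours afterwards.

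**How participants are asked.** Protocol 2.9.1 (Safety) provides polls at supervised sessions: "Pre- and post-exercise session poll questions will be completed by participants during each supervised session to capture any adverse events". They look back over the interval: "to capture any adverse events during the session and since the previous supervised session". It adds: "Weekly troubleshooting after the live exercise sessions and the group behaviour change sessions will assess safety, progress, health, and any adverse effects". Protocol 1.7 describes this second route as optional: "Participants will have the opportunity to attend the troubleshooting session at least weekly". Protocol 4.3 gives the practitioner's duty as: "Checking for AEs when participants attend for exercise session or via pre- and post-exercise poll responses".

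**What exists away from sessions.** Participants have an email address and telephone number, but Protocol 4.2.2 says: "Whilst participants will not be actively encouraged to report AEs via this route". For non-attendance, Protocol 2.9.1 says: "If a participant fails to attend two consecutive intervention appointments a REGAIN practitioner will attempt to contact them via telephone or email". The stated purpose is welfare. That contact is not named in Protocol 4.2.2 or 4.3. Protocol 4.2.3 uses the three-month questionnaire in both arms to pick up possible SAEs.

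**What is reported.** SAP 6 says: "The frequency and percentage (%) of serious adverse events (SAE) and adverse events (AE) in the trial will be reported by treatment". It mentions neither sessions attended nor whether a participant was still being asked.

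**The concern.** The recording duty follows exercise, including unsupervised exercise at home. The means of asking follow attendance at a live or group session. The two separate when someone leaves the sessions, and leaving may itself result from the exercise. A participant who feels well when the post-session poll closes, becomes unwell that evening and does not come back has had a recordable event, but no specified question would find it.

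This matters because non-serious AEs are not sought in usual care (Protocol 4.2.1). The intervention-arm figure is thus the trial's only measure of non-serious exercise harm. In a simple frequency and percentage, a person who left and was not asked again looks the same as a person who was asked and had no event. If the reason for leaving was an event, the loss is informative and lowers the figure.

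**Working it through.** The plan states no figure on this point, so the check sets the recording duty against the enquiry routes, case by case.

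| Non-serious event, intervention arm | Recordable under 4.2.1? | Specified active question |
|---|---|---|
| During a live session | Yes | That session's post-exercise poll |
| Within 24 hours after a live session, or tied to an on-demand session; participant returns to live exercise | Yes | Next poll, through its look-back |
| Same; participant drops exercise sessions but attends psychological groups | Yes | Troubleshooting after the group (optional) |
| Within 24 hours after the last session attended; participant returns to neither | Yes | None beyond the attempted welfare contact, whose content is not stated |
| In, or within 24 hours of, an on-demand session done after the last attended session | Yes | None beyond the same contact |
| More than 24 hours after all exercise has stopped | No | Not needed |

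The gap is the fourth and fifth rows.

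**On-demand exposure is planned.** SAP 2.5.1 has two to three exercise sessions a week, one of them live and the remaining one or two pre-recorded. Use of the videos after leaving the live group is therefore possible, and Protocol 2.9.2 records clicks and viewing time.

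**The welfare contact does not close the gap as written.** It is an attempt. It has no stated AE question. It also needs two consecutive missed appointments, so someone who leaves with only one appointment remaining cannot trigger it.

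**Serious events are different.** The three-month questionnaire does not depend on attendance, and Protocol 4.4 seeks deaths from the GP records of 12-month non-responders.

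**Effect on the reported percentage.** Read SAP 6 as a percentage of participants. Let N be the number in the intervention arm and k the number with a recorded AE. Let u be the number with an in-window AE in rows four or five and no recorded AE.

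- Reported: k/N. Including the missed events: (k + u)/N. Shortfall: u/N.
- Each such participant is worth 1/N. At the planned N of 272 (SAP 2.8), that is 1/272 = 0.37 percentage points.
- For early stoppers, u cannot exceed S, the number who stopped before the end of the programme, have no recorded AE and were not asked after their last attended session. So 0 ≤ u ≤ S.

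Neither document gives u, S, attendance or the success rate of the welfare contact. The shortfall therefore has a known form and an unknown size. Reporting S would bound it.

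**The case against.** The strongest case against has four parts.

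1. **The documents do not abandon those who stop.** Contact is attempted after two misses, SAEs are sought at three months, people who remain in the psychological groups are still asked, and a missed week followed by a return is covered by the look-back. All of this stands. A reader might infer that enquiry ends for anyone who stops exercising; these provisions contradict that.

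2. **The 24-hour window limits what can be missed.** This also stands. Someone who has stopped all exercise soon has no further recordable AEs, so their remaining programme weeks are not missed observation. A reader might want to state a share of programme time left uncovered, or a rate per participant-week. Either would count unexposed time.

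3. **An in-window event disclosed in a welfare call could already be logged.** Protocol 4.2.1 does not restrict how an event comes to light. Protocol 2.6 has willingness to continue monitored and a reason for withdrawal noted if offered, and Protocol 2.8.2 has a withdrawal form completed. This stands in part: such events may be logged if volunteered. None of these provisions asks the question.

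4. **The misreading is speculative.** No week-by-week AE display is planned, the DMC sees compliance beside safety data, and SAP 4.4 reports adherence. It is right that the documents do not support a claim that counts fall over the eight weeks, or that readers would see improving tolerability. Adherence reported separately still does not show who was not asked after leaving.

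**Conclusion.** The point holds in a limited form. For people who stop attending live and group sessions, non-serious AEs in the 24 hours after the last session, or tied to later on-demand sessions, fall within the protocol's recording duty. They have no specified active enquiry beyond one attempted contact with no stated AE content. The AE percentage in SAP 6 may be too low for that reason.

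The direction rests on two assumptions: that some people stop because of such events, and that the welfare contact does not routinely ask about them. The documents confirm neither and do not allow the size to be estimated. Serious events are largely protected, and the primary efficacy analysis is not affected. This is an inexpensive improvement to harms ascertainment and reporting, not a failure of safety oversight.

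**What to change.** **(1) Protocol 2.9.1, 4.2.2 and 4.3.** Name the contact after two consecutive missed appointments as a source of AEs. Ask the existing poll question for the period since the last attended session, stating that on-demand sessions are included, and log the answer, including a negative one. Ask the same question when a withdrawal form is completed.

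**(2) SAP 6.** Report intervention-arm AEs beside the number of live sessions attended and the on-demand use, not as a rate per participant-week. State how many participants stopped before the end of the programme with no AE enquiry after their last attended session and, of those, how many viewed on-demand exercise videos later.

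**Cost.** Part (1) takes slightly more practitioner time and may raise the AE count in the intervention arm. Part (2) uses the attendance and viewing logs in Protocol 2.9.2. Attendance is not the same as poll completion, and neither document says welfare contacts are logged, so the SAP should state how enquiry after the last session was determined. SAP 2.8 says recruitment is complete at 585. If delivery has also ended, only part (2) applies.

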2.9.2 Compliance

Compliance with REGAIN intervention: Attendance at live online exercise sessions and the psychological support sessions will be logged by the online platform for each participant every week. Participants will be identified using their email address. Data will also be recorded detailing the number of times an individual has clicked onto an online video and the amount of time they have spent viewing each video. The completion of intervention (individual assessment, online live exercise sessions, psychological support sessions and online and guided home exercise plan,) and control sessions will be recorded as one measure of compliance.

Definition of compliance with intervention

The impact of compliance on outcomes will be assessed using a CACE (compliers average causal effect) analysis. A detailed statistical analysis plan will be written and approved by the Data Monitoring Committee (DMC) including definitions of full and partial compliance for the intervention group.

Fidelity: The majority of live exercise sessions and psychological support sessions will be audiorecorded (practitioner only) to reduce the risk of those delivering the intervention behaving differently when being recorded. The psychological support sessions will be audio-recorded and scored against criteria. From these sessions, a purposively selected subset (10%) of recordings will be analysed across relevant intervention sessions. This will enable assessment of fidelity, and an understanding of areas and issues that generated discussion.

The control group individual practitioner appointment will also be audio recorded and scored against criteria.

2.10 Concomitant illness and medication

2.10.1 Concomitant illness

At the start of the study, potential participants will be screened during their eligibility assessment for any concomitant illnesses. If the illness influences the potential participant's eligibility to continue in the study (e.g. serious mental health problems that preclude participation in a group intervention) the investigator will be informed and they will not be eligible to participate.

2.10.2 Concomitant medication

Participants will be asked to record any medications they are taking, for COVID related problems, at each follow-up time point (baseline, three, six and 12 months).

2.11 Co-enrolment into other trials

Co-enrolment of REGAIN participants onto other interventional studies will be considered where there is no possible conflict with the REGAIN study objectives. A list of appropriate and agreed studies will be produced at a national level to guide co-enrolment. In addition, the CI will review the protocols for other studies at sites e.g. interventional studies and will consider co-enrolment in conjunction with the Trial Management Committee where appropriate.

2.12 End of study

The study will end when all participants have completed their 12-month follow-up. As part of the process evaluation, n=25 participants in the control arm and n=25 from the intervention arm will be interviewed **after** their three-month follow-up.

The study will be stopped prematurely if:

- Mandated by the Ethics Committee
- Following recommendations from the Data Monitoring Committee (DMC)
- Funding for the study ceases

The Research Ethics Committee will be notified in writing within 90 days when the study has been concluded or within 15 days if terminated early.

3. METHODS AND ASSESSMENTS

3.1 Schedule of delivery of intervention and data collection

Table 1. Study assessments

	Pre-randomisation		Post-randomisation				
Online assessment	1	2	3	4	5	6	
Assessment time point	Screening	Enrolment/ randomise (Baseline)	Intervention Delivery	3m (± 2w)	6 m (± 1 m)	12 m (± 1 m)	
Invitation letter and flyer posted	~						
Initial Eligibility Assessed	~						
Concomitant Illnesses		~					
Eligibility check* (telephone)		~					
Informed consent		~					
Patient Demographics		~					
Medication Use				~	✓	\checkmark	
PROMIS [®] 29+2 Profile v2.1 (PROPr)		~		~	~	✓	
PROMIS dyspnoea		~		~	√	~	
PROMIS Neuro- QoL		~		~	√	~	
EQ-5D-5L		✓		~	~	✓	
IPAQ-SF		✓		~	~	\checkmark	
IES-R		✓		~	~	\checkmark	
HADS		✓		~	~	\checkmark	
Work status		✓		~	~	\checkmark	
Intervention			✓				
Adverse events			✓				
Overall health		✓		~	~	\checkmark	
Death						\checkmark	
Health and Social Care resource use				✓	✓	~	

	Pre-rar	ndomisation	Post-randomisation				
Online assessment	1	2	3	4	5	6	
Assessment time point	Screening	Enrolment/ randomise (Baseline)	Intervention Delivery	3m (± 2w)	6 m (± 1 m)	12 m (± 1 m)	
Semi-structured interviews (Process evaluation)				~			

* Eligibility check will be performed in person over the telephone by clinical member of the research team at UHCW. All other assessments and information will be completed by the participant online.

3.2 Long term follow-up assessments

Long-term follow-up: Consent will be sought from participants to keep their personal data, and at the end of the study follow-up period request a copy of the participant's medical record from their GP if the participant has not responded to the 12-month follow-up or if we know the participant has died. This will provide information on GP consultations and include copies of any hospital discharge letters allowing us to accurately cost in-patient care costs. Mortality data will be gathered from GP records at 12 months.

3.3 Symptoms sub-study

PIC sites will be asked to send information to WCTU on recorded ethnicity, age, gender, duration of hospital stay and type of ventilation received for any participants that complete an initial screen form and provided consent for this. This data will be sent to WCTU in a pseudonymised format with the participant identified using the screening ID number.

These data will not be collected from those patients screened via the self-referral route of study entry.

3.4 Embedded process evaluation

Semi-structured interviews with participants: Information about interviews will be provided to all participants during study recruitment. Participants will be asked to consent (or not) to being contacted around three months after they have entered the study to share their views and experiences of the intervention and control. Participant interviews will be completed online and online verbal consent will be taken and documented prior to the interview taking place.

Interviews will be conducted by a qualitative Research Fellow from WCTU, on the phone/video-call as appropriate.

Pilot study

Interviews with up to five people in each arm recruited to the internal pilot to check intervention acceptability, and identify obstacles or facilitators to participation, uptake and completion. We will

use this internal pilot to optimise recruitment and retention by identifying challenges, and solutions which will be discussed with our patient partners. The model used for interviews in the pilot study will differ from the main study in that participants will be interviewed within three months of randomisation rather than after three months.

Main Study

Intervention and control participants will be interviewed to investigate their experiences, contextualise quantitative findings, and explore factors that helped or hindered participation, thus informing interpretation and wider implementation. Interviews will take place after the three month follow-up outcome data collection, so that the interview itself does not introduce bias to the analysis. A purposive sample of up to n=25 intervention and n=25 control participants will be interviewed at three months post randomisation to ensure a diverse range of perspectives are included. Our sample size of up to 25 per group follows guidance [36] indicating that while code saturation ('when researchers have *heard it all'*) was reached at nine interviews, 16 to 24 interviews were needed to reach meaningful saturation ('*to understand it all'*). The interviews will use a topic guide that will include participant experiences of COVID-19, and any obstacles or enablers to participation, adherence and recovery. We will explore what components were used/dropped/never used, and views on the guided home exercise content. The interviews will last about one hour, be digitally recorded on an encrypted recorder.

We will aim to include up to three participants per arm who do not speak English in our interviews. They will be interviewed by staff who have interviewing skills and relevant language skills. They will be interviewed in their first language, this will be transcribed verbatim. The transcript will then be translated into English, then back translated and the back translation compared to the original transcript. This approach will be informed by recent work in this area [37-42].

Practitioner interviews: At the end of the study, all consenting REGAIN practitioners will be interviewed (~n=5) about their experiences of delivering the interventions/best usual care, what worked well, what helped, and what was challenging. These interviews will last up to one hour, be digitally recorded, and piloted during the internal pilot.

